7.1.2. Criteria for Permanent Discontinuation of Study Intervention

In rare instances, it may be necessary for a participant to permanently discontinue (definitive discontinuation) study intervention. If study intervention is definitively discontinued, the participant will be encouraged to remain in the study. See the SoA for data to be collected at the time of discontinuation of study intervention and follow-up and for any further evaluations that need to be completed.

Permanent discontinuation of study intervention should occur if the scenarios described occur during the study.

Participant decision

- The participant requests to discontinue the study intervention.

Investigator decision

- The investigator decides that the participant should be discontinued from the study intervention.

Pregnancy

- The participant becomes pregnant during the study (see Section 8.3.5 and Section 10.4, Appendix 4).

Safety considerations

The participant:

- Has a malignancy (except for successfully treated basal or squamous cell skin carcinoma)
- Answered "yes" to Question 4 or Question 5 on the "Suicidal Ideation" portion of the C-SSRS
- Answered "yes" to any of the suicide-related behaviors on the Suicidal Behavior portion of the C-SSRS
A psychiatrist or appropriately trained professional may assist in the decision to discontinue the participant.
- Is diagnosed with LTBI during the study and are not a candidate for treatment as described in Section 7.1.1.1, or
- Has a serious or opportunistic infection that in the opinion of the investigator merits the study intervention being discontinued. Such infections may include, but are not limited to:
 - HIV/acquired immune deficiency syndrome (AIDS) infection
 - active TB infection or untreated LTBI (see Sections 7.1.1 and 8.2.6)
 - HCV RNA positive (Section 8.2.8)
 - HBV DNA positive (Section 8.2.7).

The participant should be referred to, evaluated and managed by a specialist physician with expertise in evaluation and management of viral hepatitis prior to discontinuation of any

immunomodulatory and/or immunosuppressive therapy, including study intervention. Timing of discontinuation from study intervention relative to the initiation of any antiviral treatment for hepatitis is to be based on the recommendation of the consulting specialist physician, in conjunction with the investigator, and aligned with medical guidelines and standard of care.

Hepatic event or liver test abnormality

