9.4.7. Other Safety Analyses

Analyses/measures	Presented...
Safety analyses: AEs, SAEs, C-SSRS, vital signs, ECGs, and laboratory analytes	Descriptively summarized by treatment group, will use the safety population data
Categorical safety measures	Summarized with counts by visit
Continuous safety measures	Summarized as mean change by visit
Exposure to study intervention	Calculated for each participant and summarized by treatment group by treatment period

Adverse events

Adverse events will be coded according to the Medical Dictionary for Regulatory Activities (MedDRA) and summarized by system organ class, preferred term, severity, and relationship to the study intervention. All AEs, including pre-existing conditions, will be listed by participant, visit, preferred term, treatment group, severity, and relationship to the treatment.

Treatment-emergent adverse events

A TEAE is defined as an event that first occurred or worsened in severity after baseline, with baseline defined as all pre-existing conditions recorded at Visit 1 and any AEs recorded before the first dose of study intervention (that is, during the interval between Visits 1 and 2 and recorded with the time of onset before the first dose of study intervention). For events that are gender specific, the denominator and computation of the percentage will include only participants from the given gender.

The number and percentage of participants who experienced TEAEs, TEAEs by maximum severity, deaths, SAEs, TEAEs related to study intervention, discontinuations from the treatment due to an AE, and AESIs will be summarized. Treatment-emergent adverse events (all, by maximum severity), SAEs including deaths, and AEs that lead to treatment discontinuation will be summarized and analyzed by MedDRA system organ class and preferred term.

Treatment-related TEAEs (TEAEs related to study intervention) are defined as events that are indicated by the investigator on the eCRF to be related to treatment.

Adverse events of special interest will be identified by a standardized MedDRA query or a Lilly-defined MedDRA preferred term listing.

Suicide-related thoughts and behaviors

Suicide-related thoughts and behaviors occurring during treatment will be summarized based on responses to the C-SSRS consistent with the C-SSRS Scoring and Data Analysis Guide (Columbia Lighthouse Project WWW).

Follow-up emergent adverse events

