Follow-up emergent AEs, SAEs including deaths, and AEs that lead to study discontinuation will be summarized.

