4.6.2. Adverse Events

A treatment-emergent adverse event (TEAE) is defined as an event that first occurred or worsened in severity after baseline, with baseline defined as all pre-existing conditions recorded at Visit 1 and any AEs recorded before the first dose of study intervention (that is, during the interval between Visits 1 and 2 and recorded with the time of onset before the first dose of study intervention). The MedDRA Lowest Level Term (LLT) will be used in the treatment-emergent computation. The maximum severity for each LLT before the first injection will be used as baseline. Start date of adverse events will be compared with date of first injection and the date of Visit 10 (Week 24) to determine whether an adverse event is treatment-emergent. Should there be insufficient data for adverse event start date or severity to make this comparison; the adverse event will be considered treatment-emergent.

TEAEs will be coded according to established Medical Dictionary for Regulatory Activities (MedDRA) terms and summarized by MedDRA System Organ Class (SOC) and Preferred Term.

An overview of adverse events will summarize the percentage of patients experiencing deaths, SAEs, AEs reported as reason for discontinuation, TEAEs, and AEs possibly related to study treatment.

The frequency and percentage of patients with the following will be summarized using MedDRA Preferred Term nested within SOC.

- TEAEs
- TEAEs by maximum severity
- TEAEs related to study intervention
- TEAEs leading to study discontinuation
- SAEs including death
- SAEs by maximum severity
- SAEs related to study intervention
- Deaths
- AE of Special Interests (AESIs)

Events will be sorted alphabetically by SOC and then by decreasing total frequency within SOC. For incidence counts, each patient will be counted only once within each Preferred Term and within each SOC. Percentages will be based on the number of patients in a particular treatment arm. For events that are gender-specific, the denominator and computation of the percentage will include only patients from the given gender.

Adverse events of special interest will be identified by a standardized MedDRA query or a Lilly-defined MedDRA preferred term listing.

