By-patient listings of all adverse events (including non-treatment-emergent events) recorded on the CRF, all TEAEs, TEAEs leading to study discontinuation, SAEs including death, and deaths during the Treatment Period will be presented by participant, visit, preferred term, treatment group, severity, and relationship to the treatment.

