4.9. Changes to Protocol-Planned Analyses

There is no change to protocol-planned analyses.

5. Sample Size Determination

Approximately 80 participants will be randomly assigned to study intervention. At the completion of the study, approximately 40 participants will have been randomized to LY3462817 700 mg and 20 participants will have been randomized to LY3462817 300 mg and placebo during the double-blind treatment. All randomized participants in FAS will be considered evaluable.

Assuming -1.80 and -0.75 as the DAS28-CRP change from baseline for LY3462817 700 mg and placebo, respectively, with standard deviation equal to 1.25, a 2-sided t-test with alpha = 0.05 has greater than 80% power to detect a statistically-significant difference in DAS28-CRP change from baseline at Week 12.

6. Supporting Documentation

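### The SAP tabulates and lists adverse events leading to study discontinuation where the protocol plans treatment discontinuation, so participants who stop drug for an adverse event but stay in the study can be omitted

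*SAP*

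**What the plan says.** **Protocol.** Section 9.4.7 plans a count of participants who discontinue treatment because of an adverse event (AE). It also plans a breakdown by MedDRA term: "AEs that lead to treatment discontinuation will be summarized and analyzed by MedDRA system organ class and preferred term". Among the AE summaries, study discontinuation appears only under the follow-up emergent heading: "Follow-up emergent AEs, SAEs including deaths, and AEs that lead to study discontinuation will be summarized".

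Section 7 treats stopping drug (7.1) and leaving the study (7.2) separately. Section 7.1.2 says: "If study intervention is definitively discontinued, the participant will be encouraged to remain in the study". Under Section 7.1 such a participant has an early termination visit and then visit V801. Section 4.1 places the last visit 12 weeks after the last dose.

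**SAP.** Section 4.6.2 lists "TEAEs leading to study discontinuation" among the tables by system organ class and preferred term. The by-patient listings cover "all TEAEs, TEAEs leading to study discontinuation, SAEs including death, and deaths during the Treatment Period", as well as all AEs on the CRF. The AE overview has a row for "AEs reported as reason for discontinuation", which does not say whether drug or study is meant. The SAP names no table of AEs leading to treatment discontinuation. Section 4.9 states: "There is no change to protocol-planned analyses".

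**The concern.** The SAP replaces one event with another without declaring it. Someone who stops LY3462817 or placebo because of an AE and stays for follow-up meets the protocol's definition. Unless the CRF also records a study discontinuation, that person does not meet the SAP's. A programmer who follows the SAP would leave the person out of both the table and the listing.

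Safety and tolerability compared with placebo is a secondary objective, and AEs that make people stop the drug are an output the protocol asks for by name. In arms of about 40, 20 and 20, one or two omitted participants visibly change a percentage.

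**Working it through.** The documents give no rate of AE-related discontinuation, so there is no stated figure to reproduce. The check is a comparison of the texts, followed by arithmetic on arm size.

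**1. Level used for each output**

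| Output | Protocol 9.4.7 | SAP 4.6.2 |
|---|---|---|
| Participant count or overview row | Treatment | Not stated |
| Table by organ class and preferred term | Treatment | Study |
| By-patient discontinuation listing | None separate; all AEs listed | Study |
| Follow-up emergent AEs | Study | Not separately named |

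**2. Whether the two events can differ.** They can. Protocol 7.1, 7.1.2 and 4.1 keep a participant under follow-up after drug is stopped. SAP 4.3.2 itself uses treatment discontinuation to decide which efficacy data to exclude, so it recognises the event but gives it no AE table.

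**3. Direction.** Protocol 7.2 says that leaving the study also ends study intervention. In Period 1, a participant still on drug who leaves the study for an AE has therefore also stopped drug for it, and the SAP count cannot exceed the protocol's. The argument is not strict for someone already off drug. In Period 2, for example, a participant moved to standard of care at Week 14 could leave the study for an event and enter the SAP row without having stopped drug for an AE.

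**4. Weight of one participant.** Arm sizes are from Protocol 9.2.
- 700 mg: 1/40 = 2.5 percentage points.
- 300 mg or placebo: 1/20 = 5 percentage points.

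**5. Illustration.** Let n be the arm size, d the proportion who stop drug for an AE, and s the share of those who are not recorded as leaving the study. Both d and s are assumptions.
- Protocol row, expected count: n × d
- SAP row, expected count: n × d × (1 − s)
- Shortfall: n × d × s
- Chance that the SAP row is empty: (1 − d(1 − s))^n

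For n = 40 and d = 10%, the protocol row expects 40 × 0.10 = 4.0 participants.

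| s | SAP row, expected | Shortfall | Chance SAP row is empty |
|---|---|---|---|
| 0% | 4.0 | 0 | 0.90^40 = 1.5% |
| 25% | 3.0 | 1.0 | 0.925^40 = 4.4% |
| 50% | 2.0 | 2.0 | 0.95^40 = 12.9% |
| 75% | 1.0 | 3.0 | 0.975^40 = 36.3% |
| 100% | 0 | 4.0 | 100% |

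With d = 5% the protocol row expects 2.0 and the SAP row anything from 2.0 down to 0. With d = 15% the figures are 6.0, and 6.0 down to 0.

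**The case against.** **The two rows may coincide.** Participants who stop drug go through early termination procedures, the Schedule of Activities has a single early-discontinuation column, and Protocol 4.4 counts as completers only those who finish every required phase. The CRF may therefore record these people as study discontinuations. This stands: the documents do not settle the coding, so an under-count is possible but not shown.

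**The overview row may carry the protocol's count.** Since the SAP declares no change, its unspecified row can fairly be read at treatment level, which would leave the headline percentage intact. This stands in part. The row is ambiguous, and it gives no breakdown by organ class and preferred term. The all-AE listing does not clearly fill the gap: its stated contents are participant, visit, term, arm, severity and relationship, not whether drug was stopped. Disposition (SAP 4.2) gives percentages for study withdrawal, and its listing of reasons does not state the level.

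**The numbers may be small.** Protocol 7.1.2 expects permanent discontinuation to be rare. Section 2.2 reports no AE-related discontinuation in the earlier studies, in which 47 + 6 + 7 = 60 people had received the drug. Zero of 60 gives a one-sided 95% upper limit of 1 − 0.05^(1/60) = 4.9%. Those were healthy volunteers and people with psoriasis, mostly given single doses, so this is context only. It does suggest that the 10% used above may be high.

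**It may be a drafting slip.** SAP 4.6 still contains template text, and its AE subsections point to section numbers that do not exist in this SAP. The SAP is also based on a protocol dated 05AUG2020, while the protocol reviewed here includes September 2020 data. The visible part of the change summary lists edits to 9.2, 9.4.1 and 9.5 but none to 9.4.7. A slip is plausible, but the text still has to be put right.

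**A stronger inference that fails.** A reader might conclude that the substitution flatters the drug. Placebo participants who stop drug and stay are omitted too, so the contrast shifts in the drug's favour only if such omissions are proportionately more common on LY3462817. Nothing in the documents shows that.

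**Conclusion.** The mismatch is established by the texts: the SAP table and listing use study discontinuation, the protocol plans treatment discontinuation, and no change is declared. As written, the SAP outputs can omit participants in any arm who stop study intervention for an AE without being recorded as leaving the study. For participants still on drug in Period 1 the error can go only one way, towards fewer.

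The size is not known. It depends on how often AEs lead to stopping drug, how many of those participants stay, and how the CRF codes them. It ranges from zero up to the loss of every such participant, at 2.5 points each on 700 mg and 5 points each on 300 mg or placebo.

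The documents do not support saying that the table does under-count, that the comparison is biased towards the drug, or that this is the trial's main tolerability measure. The secondary endpoint is safety assessments in general and does not name discontinuation.

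**What to change.** In SAP Section 4.6.2:

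- Define the table and the by-patient listing as *TEAEs leading to permanent discontinuation of study intervention*.
- Define the overview row on discontinuation at treatment level, as in Protocol 9.4.7.
- Keep AEs leading to study discontinuation as a separate row, and for the follow-up period as the protocol plans.

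If the sponsor does intend study discontinuation, SAP 4.9 should say so and give the reason.

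The cost is SAP wording and one extra table shell, with no change to the design. The reported AE-related discontinuation rate may be slightly higher than under the present wording.

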4.6.2.1. Hypersensitivities

Hypersensitivities will be defined using the following terms:

- Anaphylactic reaction standardized MedDRA query (SMQ) excluding the Preferred Term Anaphylactic transfusion reaction
- Angioedema SMQ excluding the Preferred Terms Oedema neonatal and Peripheral oedema neonatal
- Severe cutaneous adverse reactions SMQ Narrow Search terms and the following Broad Search terms:
 - Drug eruption
 - Drug rash with eosinophilia and systemic symptoms
 - Lip exfoliation
 - Mucosal exfoliation
 - Penile exfoliation
 - Skin exfoliation

- Stomatitis
 - Tongue exfoliation
 - Vaginal exfoliation
- Additional Preferred Terms including:
 - Asphyxia
 - Dermatitis
 - Dermatitis allergic
 - Dermatitis atopic
 - Dermatitis contact
 - Diastolic hypotension
 - Eczema
 - Eosinophilic oesophagitis
 - Erythema nodosum
 - Hypotension
 - Immediate post-injection reaction
 - Injection related reaction
 - Orthostatic hypotension
 - Photosensitivity allergic reactions
 - Photosensitivity reaction
 - Presyncope
 - Rash vesicular
 - Reaction to drug excipients
 - Red man syndrome
 - Serum sickness
 - Serum sickness-like reaction
 - Syncope
 - Type II hypersensitivity
 - Type III immune-complex-mediated reaction
 - Type IV hypersensitivity reaction
 - Toxic skin eruption
 - Urticaria contact
 - Urticaria vesiculosa

The frequency and percentage of patients experiencing treatment-emergent hypersensitivities will be summarized by treatment arm, maximum severity, SOC, and Preferred Term during Treatment Period. The frequency and percentage of patients experiencing treatment-emergent hypersensitivities will also be summarized by treatment arm and timing category (immediate, acute reaction, delayed reaction or reaction after more than 15 days).

Exposure-adjusted incidence rates (per 100 patient years) of treatment-emergent hypersensitivities within the following time intervals will be calculated as detailed below.

- ≥ 0 to ≤ 6 weeks since the date of first injection:

Interval start date = Date of first injection,

Interval end date = Date of first injection + 42 days.

- > 6 to ≤ 12 weeks since the date of first injection:
Interval start date = Date of first injection + 43 days,
Interval end date = Date of first injection+ 84 days.
- ≥ 24 weeks since the date of first injection:
Interval start date = Date of first injection + 85,
No Interval end date, Treatment Period planned for 24 weeks

The time to onset of first treatment-emergent hypersensitivity during the Treatment Period and the duration of each treatment-emergent hypersensitivity during the Treatment Period will also be defined and calculated in the same way.

A by-patient listing of all treatment-emergent hypersensitivities will be provided.

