2.3. Benefit/Risk Assessment

Manageable risks associated with most therapeutic monoclonal antibodies are the potential for infusion-related hypersensitivity and cytokine release reactions. The infusions in this study will be administered at a controlled rate, the study participants will be monitored closely, and adjustments in the infusion rate will be made and/or the infusion stopped, if indicated. Additional information regarding infusion reaction and hypersensitivity management options is located in Section [8.3.6](#).

No clinically significant safety concerns (including infusion or injection site reactions) were observed in Study KDAB, or have been observed in the Study KDAC as of 02 September 2020.

The efficacy of LY3462817 in RA has not been established. Participants may benefit by receiving personal health information from the physical examinations and from other routine safety assessments performed in this study.

In summary, in the context of the cumulative knowledge for LY3462817, the benefit/risk balance for this study is assessed to be acceptable for testing in Phase 2.

More detailed information about the known and expected benefits and risks and reasonably expected AEs of LY3462817 may be found in the IB.

3. Objectives and Endpoints

Objectives	Endpoints and Estimands
Comparison Groups: Placebo vs LY3462817 [time frame for endpoint evaluation: 12 weeks from randomization, unless stated otherwise]	
Primary	
To evaluate the efficacy of LY3462817 in adult participants with moderately to severely active RA	
Change from baseline in DAS28-CRP
 
The primary comparison will be assessed using a hypothetical efficacy estimand strategy to address the intercurrent event of early discontinuation where the mean change from baseline will be evaluated using only data up until discontinuation as if all subjects remained on randomized treatment.

Secondary	
To describe the safety and tolerability of LY3462817 compared to placebo	Safety assessments such as AEs, SAEs
To evaluate the effect of LY3462817 on measures of disease activity	
 • Proportion of participants achieving ACR20, ACR50, and ACR70 • Change from baseline for physician-assessed individual components: 
 ○ 68 tender joint count ○ 66 swollen joint count ○ physician's global assessment of disease activity (VAS) • Change from baseline for mean SDAI • Change from baseline for mean CDAI

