6.1. Study Intervention(s) Administered

Study interventions

Each participant will receive multiple IV infusions of placebo, LY3462817 300 mg, or LY3462817 700 mg.

Intervention Name	Placebo	LY3462817	LY3462817	
Dose Formulation	0.9% sodium chloride solution	Solution	Solution	
Unit Dose Strengths	-	50 mg/mL in a 3-mL vial		
Dosage Level(s) (mg)	Not applicable	300	700	
Use	Placebo	Experimental		
IMP and NIMP	IMP	IMP		
Sourcing	Commercially available 0.9% sodium chloride solution sourced centrally by Lilly	From Lilly		
Packaging and Labeling	Commercially available 0.9% sodium chloride solution	Study intervention will be provided in glass vials and will be labeled as required per country requirement		

Abbreviations: IMP = Investigational Medicinal Product; NIMP = Noninvestigational Medicinal Product.

Study intervention will be prepared by an unblinded pharmacy staff or pharmacist who is not involved in any other study-related procedures.

The study intervention is planned to be administered as an IV infusion.

The infusion rate may be reduced as deemed necessary if an infusion reaction is observed (Section 8.3.6). Participants will be monitored for signs and symptoms of infusion reaction:

- during the infusion, and
- for at least 1 hour after completion of the infusion.

Infusion information may be found in the pharmacy binder.

Resuscitation equipment, emergency drugs, and appropriately trained medical staff must be available during the infusion and for at least 1 hour after the completion of the infusion.

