8.3.6. Adverse Events of Special Interest

Adverse events of special interest for this study include:

- hypersensitivity
- infusion site reactions
- infections, and
- malignancy.

Hypersensitivity

Many drugs, but particularly biologic agents, carry the risk of systemic hypersensitivity reactions. If such a reaction occurs, additional data describing each symptom should be provided to the sponsor in the eCRF.

Sites should have appropriately trained medical staff and appropriate medical equipment available when study participants are receiving study drug. It is recommended that participants who experience a systemic hypersensitivity reaction be treated per national and international guidelines.

In the case of generalized urticaria or anaphylaxis, additional blood and urine samples should be collected as described in Section 10.6, Appendix 6, Recommended Laboratory Testing for Hypersensitivity Events. Laboratory results are provided to the sponsor via the central laboratory.

Infusion Site Reactions

Symptoms of a local infusion site reaction may include erythema, induration, pain, pruritus, and edema. If an infusion site event is reported, the AE will be recorded, and additional data will be provided to the sponsor in the eCRF.

Infections

Participants will be monitored for symptoms and signs of infection after administration of LY3462817. More detailed information may be found in the IB.

Opportunistic Infections

The sponsor will identify infections considered to be opportunistic based on the publication “Opportunistic infections and biologic therapies in immune-mediated inflammatory diseases: consensus recommendations for infection reporting during clinical trials and postmarketing surveillance” (Winthrop et al. 2015).

Malignancy

Participants will be monitored for symptoms and signs of malignancy after administration of LY3462817. More detailed information may be found in the IB.

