4.6.2.2. Infusion Site Reactions

Infusion site reactions will be defined using terms from the infusion site reactions high level term.

The frequency and percentage of patients with a treatment-emergent infusion site reaction will be summarized by treatment arm, maximum severity, SOC, and Preferred Term during Treatment Period.

The frequency and percentage of patients with infusion site reactions will be summarized by treatment arm and redness category (normal, noticeable but very mild redness, clearly red, bright red, and dark with some scar formation) during Treatment Period and during Treatment Period. Similarly, the frequency and percentage of patients with infusion site reactions will be summarized by treatment arm and swelling category (no bump, barely noticeable, clear bump but very thin, clear bump 1mm thick, clear bump 2mm thick or more) during Treatment. Finally, the frequency and percentage of patients with infusion site reactions will be summarized by treatment arm and pain category (none, mild, moderate and severe) during Treatment Period.

The duration of each treatment-emergent infusion site reaction during the Treatment will be defined and summarized in the same way as described for infectious AEs in Section 16.4.2.1.

A by-patient listing of treatment-emergent infusion site reactions will be provided.

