4.6.4.4. Immunogenicity

The frequency and percentage of patients with positive anti-drug antibodies (ADAs) by visit will be summarized by treatment arm. The frequency and percentage of patients with positive ADAs

at any time point during the Treatment Period (including pre-treatment visits) up to and including Visit 9 (Week 24) will also be summarized by treatment arm.

The frequency and percentage of patients with a treatment-emergent positive ADA incidence will be summarized by treatment arm. A treatment-emergent incidence is defined as a four-fold increase [2 dilution increase] in immunogenicity titer over the baseline titer during the Treatment Period. Scheduled visits, unscheduled visits, and repeat measurements will be included.

The time to the development of treatment-emergent ADAs will be calculated as:

Time to development of treatment-emergent ADAs (in weeks) = (Date of development of treatment-emergent ADAs – Date of randomization + 1) / 7.

If a patient has not developed treatment-emergent ADAs, they will be censored at the date of the last immunogenicity assessment during the Treatment Period. If they did not have an immunogenicity assessment, they will be censored at the date of first injection.

The time to development of treatment-emergent ADAs will be analyzed using a Cox proportional hazards model, with treatment arm and strata (previous RA therapy population) fitted as explanatory variables. The estimated hazard ratio, 95% confidence interval and p-value for treatment comparisons between each LY dose and placebo will be presented. A Kaplan-Meier plot of the time to development of treatment-emergent ADAs will be presented by treatment arm.

The frequency and percentage of patients with both a treatment-emergent positive ADA incidence (yes, no) and at least one treatment-emergent Hypersensitivity adverse event (yes, no) will be summarized by treatment arm. Similarly, the frequency and percentage of patients with both a treatment-emergent positive ADA incidence (yes, no) and at least one treatment-emergent injection site reaction (yes, no) adverse event will be summarized by treatment arm.

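### The written-out hypersensitivity terms name injection reactions for an infused drug and no infusion-related or cytokine-release term, so events coded only that way may miss the hypersensitivity and ADA tables

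*SAP*

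**What the plan says.** **Route.** Protocol 6.1: "The study intervention is planned to be administered as an IV infusion". The same section has participants watched for infusion reactions during and after dosing and points to protocol 8.3.6.

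**Risks.** Protocol 2.3: "Manageable risks associated with most therapeutic monoclonal antibodies are the potential for infusion-related hypersensitivity and cytokine release reactions". It continues: "Additional information regarding infusion reaction and hypersensitivity management options is located in Section" 8.3.6.

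**Special-interest events (AESIs).** In protocol 8.3.6, the list opened by "Adverse events of special interest for this study include" has four items: hypersensitivity, infusion site reactions, infections and malignancy. The infusion item is local: "Symptoms of a local infusion site reaction may include erythema, induration, pain, pruritus, and edema". Systemic infusion reaction and cytokine release are not items.

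**SAP searches.** SAP 4.6.2.1 builds hypersensitivity from three SMQs (anaphylactic reaction, angioedema, severe cutaneous reactions) plus a list of preferred terms. Two of those name injection reactions; one is "Injection related reaction". For the infusion item, SAP 4.6.2.2 says: "Infusion site reactions will be defined using terms from the infusion site reactions high level term".

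**Link to ADA.** SAP 4.6.4.4 crosses treatment-emergent ADA with hypersensitivity, and separately with "at least one treatment-emergent injection site reaction (yes, no) adverse event will be summarized by treatment arm".

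**The concern.** A preferred-term search selects on the coded term, so its exact wording decides which events are counted. Here the listed terms follow a route the trial does not use, and no listed term matches the systemic reactions that the protocol itself anticipates.

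The special-interest analyses add what the general adverse event tables lack. For hypersensitivity, SAP 4.6.2.1 plans timing categories relative to dosing, exposure-adjusted rates by interval, and time to first onset; SAP 4.6.4.4 adds the link to ADA. For an infused antibody, these are the summaries a reader would use to judge whether reactions cluster around the infusion or follow antibody formation. An event left out of the search is left out of all of them.

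The site-reaction cross-table has a separate defect. It uses an event that the SAP defines nowhere, because the event defined in 4.6.2.2 is the infusion site reaction. Read literally, the table is undefined or empty.

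**Working it through.** The plan gives no figure on this point, so the check is mainly a comparison of sections.

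**1. Where each kind of event would be counted**

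| Event as coded | Reached by a search the SAP writes out? |
|---|---|
| Anaphylaxis or angioedema | Yes: SMQs in 4.6.2.1 |
| Hypotension, syncope, presyncope, serum sickness | Yes: listed terms in 4.6.2.1 |
| Local reaction at the infusion site | Yes: high level term in 4.6.2.2 |
| Injection-related or immediate post-injection reaction | Yes: listed terms in 4.6.2.1, but worded for another route |
| Systemic infusion-related reaction, coded only as such | No listed term; depends on SMQ content or a sponsor list |
| Cytokine release, coded only as such | No listed term; depends on SMQ content or a sponsor list |

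Among the listed preferred terms there are two for injection reactions, none for infusion-related reactions and none for cytokine release. The searches for infections, malignancy and depression (4.6.2.3 to 4.6.2.5) are not aimed at these events.

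**2. What remains open.** The documents do not give the SMQ contents. The added terms are introduced as examples, so the list may not be complete. SAP 4.6.2 also allows a sponsor-defined term list for special-interest events, and that list is not in the documents. The gap is therefore in what is written out; whether it is also a gap in the final search cannot be settled here.

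**3. Where such events still appear.** SAP 4.6.2 tabulates all treatment-emergent events by system organ class and preferred term. It has further tables by severity and relatedness, and for serious events and events leading to discontinuation. By-patient listings cover every recorded event.

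**4. Where the cytokine-release gap starts.** Protocol 2.3 names the risk, but protocol 8.3.6 does not make it a special-interest event. The SAP has a section for each of the four items in 8.3.6, so here it follows the protocol's list. Protocol 2.3 and 6.1 both refer to 8.3.6 for infusion reactions, yet the text there deals with systemic hypersensitivity and local site reactions only.

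**5. Illustration of size.** Planned active participants: 40 + 20 = 60. The Schedule of Activities has dosing at Weeks 0, 4, 8 and 12, so at most 60 × 4 = 240 active infusions by Week 12. The documents give no reaction rate. For an assumed proportion *p* of participants with at least one such event, the expected number is 60*p* and the chance of at least one is 1 − (1 − *p*)^60:

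- *p* = 2%: 1.2 expected; 70% chance of at least one
- *p* = 5%: 3 expected; 95%
- *p* = 10%: 6 expected; 99.8%

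The infusion count sets the scale only and does not enter these results. How many of these participants would be missed depends on how their events are coded.

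**The case against.** The strongest reply is that systemic hypersensitivity is searched broadly. The SMQs, the blood-pressure and syncope terms and the listed hypersensitivity types would catch many infusion reactions by their symptoms or diagnosis. Protocol 8.3.6 covers systemic hypersensitivity and has symptom-level data collected for it. Generalized urticaria or suspected anaphylaxis leads to the testing in Appendix 6, which includes ADA and a cytokine panel. SAP 4.6.4.4 already crosses ADA with hypersensitivity. In a trial of about 80 people, a few infusion reactions would be visible by name and arm in the general tables. The unblinded-review triggers in protocol 9.5 rest on severe related events within a system organ class or on a malignancy, not on these searches.

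All of this stands, and it rules out two stronger readings. A reader might infer that the main risks named in protocol 2.3 fall outside every special-interest table. They do not: much of infusion-related hypersensitivity is captured, and only events coded solely to an infusion-reaction or cytokine-release term are exposed. A reader might also infer that these are the events most likely to limit dosing. The documents do not say so. Protocol 2.3 speaks of therapeutic antibodies in general and reports no clinically significant safety concern in the two earlier studies up to the data cutoff.

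It is also fair to say that the SAP uses injection loosely for dosing throughout, and that protocol exclusion criterion 39 refers to IV injections. The event in 4.6.4.4 is thus probably a slip for the infusion site reaction. That explains the wording in running text, but it does not rescue a list of search terms, where the words are the rule. Nor do the general tables supply the timing categories, interval rates or ADA link.

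**Conclusion.** The point holds in a limited form. As written, the added terms in SAP 4.6.2.1 do not fit the route of administration and omit the two reaction types that protocol 2.3 names. An event coded only to such a term is assigned to no special-interest table by any term the SAP spells out. The site-reaction cross-table in 4.6.4.4 rests on an undefined event whatever the SMQs contain.

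The practical loss is confined to the special-interest summaries and the ADA link; no event disappears from the database or the general tables. Its size cannot be derived from the documents. The 3 to 6 participants at an assumed 5% to 10% are illustrative, and they would be missed only if coded solely to unlisted terms and if neither an SMQ nor a sponsor list contained those terms. This is worth correcting before lock because the correction is specific and cheap.

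**What to change.** **SAP, before lock**

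- In 4.6.2.1, check what the three SMQs contain in the MedDRA version used. Then add preferred terms for infusion-related reaction, infusion-related hypersensitivity and cytokine release wherever they are not already covered. Report them as an identifiable line by arm, so that they can be read apart from the rest of hypersensitivity. State that the list is complete, or cite the sponsor list that completes it.
- In 4.6.4.4, replace the injection site event with the infusion site reaction defined in 4.6.2.2. Keep the hypersensitivity cross-table and run it on the expanded terms.

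**Protocol, next amendment**

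- Reconcile 2.3, 6.1 and 8.3.6 on systemic infusion reactions, so that the cross-references lead to text on that subject and the status of cytokine release is explicit.

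A separate special-interest event for systemic infusion reactions, tabulated by infusion number, is optional.

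The cost is a small edit to the term list and its programming. The hypersensitivity count becomes slightly broader, which the separate line keeps visible.
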